4.6.3.1 Primary Endpoints

PFS-6 using the RANO criteria (see Section 18.2) will be used as primary endpoints.

4.6.3.2.Secondary Endpoints

- Safety of the combination of SGT-53 and Temozolomide.
- PFS, OS
- Anti-tumor activity of the combination of SGT-53 and Temozolomide based upon the RANO criteria.
- The induction of apoptosis by SGT-53 in the tumor (optional procedure).
- Nanoparticle delivery (optional procedure)

4.6.4. Statistical hypothesis and sample size:

A total of 26 patients will be enrolled. A maximum of 6 patients will be enrolled to participate in the optional surgical resection for tumor analysis.

Patients who have received at least one dose of study drug will be considered evaluable for safety and toxicity endpoints. Patients who require a dose interruption or reduction during the initial cycle will remain evaluable for toxicities if the reduction or interruption is due to a DLT. Patients who do not complete one cycle of treatment but do not have a DLT may be replaced as described in more detail in Section 9.6.

The primary endpoint for the trial is PFS6. Progression-free survival will be defined as the time from study enrollment until the time of first occurrence of disease progression, relapse, or death due to disease.

The analysis of the biological correlate data in patients with surgical resection for tumor analysis has the overall goal of providing an increased understanding of the ability of SGT-53 to cross the Blood-brain Barrier and be delivered into tumor cells in the brain. As such, the objective of the tumor analysis is qualitative rather than quantitative. It should be noted that in the Phase I dose escalation trial of SGT-53, the presence of the exogenous wtp53 delivered by SGT-53 was found to be present in the tumors in a DNA dose dependent manner. Moreover, even the lowest dose of SGT-53 (0.6mg DNA/infusion) was not only found to be present in the tumors of the patients, but to have some anti-tumor effect. A DNA dose 6-fold higher (3.6mg DNA/infusion) is being used in this trial.

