Reverse transcription PCR to determine transgene expression is not applicable for these studies because it would not be able to unequivocally establish that the p53 protein detected was from the exogenous transgene. In contrast, since we have designed primers that included part of the plasmid vector backbone, only the exogenous DNA is amplified. This DNA PCR approach was used to detect the presence of the transgene in the tumors in the Phase I trial (See Figures 16 and 17 in Section 4.4.1.1) and will be used for these studies. The presence of at least 30 copies of exogenous p53 in the tumors sample will be considered positive evidence of drug penetration.

All of the patients in the trial will receive the same dosing of the combination of SGT-53 and TMZ (6 doses of SGT-53 and 5 doses of TMZ every 4 weeks for three 4 week cycles) and thus patients with or without surgical resection for tumor analysis will be used for the Simon two stage calculation. Even for the patients who undergo the optional surgical resection for tumor analysis PFS6 is the primary endpoint. No TMZ will be administered during the time these patients receive the two doses of SGT-53 prior to the resection. Exogenous p53 expression is transient. The patients who receive surgery will not begin treatment for 2-3 weeks post-surgery. Previous studies have demonstrated that there is no indication of the exogenous wtp53, even by DNA PCR, after this length of time. Thus, there will be no additional residual DNA present from the two pre-surgery doses of SGT-53 by the time the combination therapy being evaluated is initiated.

According to the Simon Minimax design, our study, with its sample size of n = 26, has a 10% probability of rejecting (a) the hypothesis of a PFS6 15% (P0) (the historical PFS6 rate) and a 70% probability of accepting (1-b) the hypothesis of a PFS-6 of 30% (P1). If two, or fewer of the first 18 patients were progression free at 6 months, PFS-6 would be considered <15% and the study terminated. Otherwise, the study would be completed, the accrual target being 26 patients. If six or fewer of the 26 patients were progression-free at 6 months, then no further investigation of the treatment regimen would be considered warranted. PFS6 and secondary endpoints progression free survival and overall survival will be evaluated using the Kaplan-Meier product-limit survival curve methodology.

4.6.5. Study Objectives:

Primary:

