10.4. Efficacy Assessments

10.4.1. Progression-Free Survival

The percentage of patients who are alive and progression-free clinically and radiologically 6 and 12 months after starting treatment will be evaluated using the Kaplan-Meier method. Progression is defined by any of the following using the RANO criteria:

- a) >25% increase in sum of the products of perpendicular diameters of enhancing lesions compared with the smallest tumor measurement obtained either at baseline (if no decrease) or best response, on stable or increasing doses of corticosteroids*.
- b) Significant increase in T2/FLAIR non-enhancing lesion on stable or increasing doses of corticosteroids compared with baseline scan or best response after initiation of therapy *not caused by co-morbid events (e.g. radiation therapy, demyelination, ischemic injury, infection, seizures, postoperative changes, or other treatment effects)
- c) Any new lesion

- d) Clear clinical deterioration not attributable to other causes apart from the tumor (e.g. seizures, medication adverse effects, complications of therapy, cerebrovascular events, infection, and so on) or changes in corticosteroid dose
- e) Failure to return for evaluation as a result of death or deteriorating condition
- f) Clear progression of non-measurable disease

Note: All measurable and non-measurable lesions must be assessed using the same techniques as at baseline.

*Stable doses of corticosteroids include patients not on corticosteroids.

10.4.2. Tumor response rate:

The percentage of patients with a complete or partial response 6 and 12 months after starting treatment will be evaluated using the RANO criteria:

Complete response (CR). Requires all of the following

- a) complete disappearance of all enhancing measurable and non-measurable disease sustained for at least 4 weeks
- b) no new lesions
- c) stable or improved non-enhancing (T2/FLAIR) lesions
- d) patients must be off corticosteroids (or on physiologic replacement doses only)
- e) stable or improved clinically

Note: Patients with non-measurable disease only cannot have a complete response; the best response possible is stable disease.

Partial response (PR). Requires all of the following:

- a) >50% decrease compared with baseline in the sum of products of perpendicular diameters of all measurable enhancing lesions sustained for at least 4 weeks
- b) No progression of non-measurable disease
- c) No new lesions

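### The primary endpoint PFS6 is defined in two conflicting ways, in Sections 4.6.4 and 10.4.1, and nothing says which governs

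*Combined protocol and SAP*

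**What the plan says.** Section 4.6.3.1 states that "PFS-6 using the RANO criteria (see Section 18.2) will be used as primary endpoints". The Section 18.2 table summarises response categories and gives neither a time origin nor a rule for deaths.

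Section 4.6.4 repeats that PFS6 is primary and defines progression-free survival as "the time from study enrollment until the time of first occurrence of disease progression, relapse, or death due to disease". The same section holds the decision rule. The trial stops if two or fewer of the first 18 are progression-free at 6 months, and "If six or fewer of the 26 patients were progression-free at 6 months" the regimen is not pursued. The null rate is described only as "the hypothesis of a PFS6 15% (P0) (the historical PFS6 rate"), with no clock or event definition. The section then adds that "PFS6 and secondary endpoints progression free survival and overall survival will be evaluated using the Kaplan-Meier product-limit survival curve methodology".

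Section 10.4.1, headed Progression-Free Survival, reads differently: "The percentage of patients who are alive and progression-free clinically and radiologically 6 and 12 months after starting treatment will be evaluated" by Kaplan-Meier. Item (e) of its progression list is "Failure to return for evaluation as a result of death or deteriorating condition", with no limit on cause. Sections 10.4.3 (time to progression) and 10.4.4 (overall survival) both run from treatment initiation.

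Patients having the optional resection receive SGT-53 on Days -3 and -1. Section 4.6.4 says of them: "The patients who receive surgery will not begin treatment for 2-3 weeks post-surgery". Section 5 sets their cycle 1 Day 1 at the first infusion after surgery. Neither section says that this date is the origin for PFS.

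**The concern.** The two definitions differ in both parts of a time-to-event endpoint: when the clock starts and which deaths are events. This is the sole primary endpoint, and it feeds a go/no-go rule in which one patient's classification can reverse the decision (2 against 3 of 18, or 6 against 7 of 26).

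The death rule matters most for a patient who dies before 6 months, without documented progression, from something other than the tumour. Section 10.4.1 makes that patient a failure. Section 4.6.4 read literally does not make the death an event, and no passage says who decides whether a death was due to disease for PFS. The study is open-label, so the choice could be made after outcomes are known.

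The clock matters in both directions. For patients who are event-free at first dose, starting at enrolment shortens the treated part of the 6-month window, so PFS6 can only rise or stay the same. A progression or disease death between enrolment and first dose, however, is a failure only under the enrolment clock.

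**Working it through.** **Inputs from Section 4.6.4.** Stage 1 has 18 patients and continues with at least 3 progression-free. The final analysis has 26 and needs at least 7. The null rate is 15% and the alternative 30%, with a stated 10% false-go probability and 70% power.

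**The plan's own figure.** With X the stage-1 count, P(go) = Σ (x = 3 to 18) P[Bin(18, p) = x] × P[Bin(8, p) ≥ 7 − x].

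- p = 0.15: P(go) = 0.0826, with probability 0.480 of stopping at stage 1.
- p = 0.30: P(go) = 0.7007.

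A minimax search at 10% and 70% returns 2/18 and 6/26. The design is therefore right, and the issue is what is being counted.

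**Assumption for the death rule.** The documents give no rate of non-disease death, so take k = 1, 2 or 3 expected among 26 before 6 months and without progression: k/26 = 0.038, 0.077, 0.115.

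**Case A: true any-death PFS6 is 15%.**

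- *Deaths are failures.* p stays 0.15, so P(go) = 0.083 for every k.
- *Deaths are censored.* Use exponential times with total hazard −ln(0.15) = 1.897 per 6 months. Non-disease deaths make up (k/26)/0.85 = 0.045, 0.090, 0.136 of all events. The Kaplan-Meier curve then targets 0.15^(1 − share) = 0.163, 0.178, 0.194, which is 1.3, 2.8 and 4.4 points above 0.15. To get a decision from it, the estimate was held to 3/18 at stage 1 and 7/26 at the end. This rule is an assumption and is not in the protocol. With 400,000 simulated trials, P(go) is about 0.098, 0.133 and 0.184, and repeat runs give up to 0.186 for k = 3.

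**Case B: the 15% and 30% rates exclude non-disease deaths, but all deaths are counted.** Let a = −ln(0.15) = 1.897 or −ln(0.30) = 1.204 be the disease hazard. Solve for the other-cause hazard b in [b/(a + b)] × [1 − exp(−(a + b))] = k/26. The any-death rate is exp(−(a + b)).

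| k | p from 15% | P(go) | p from 30% | P(go) |
|---|---|---|---|---|
| 1 | 0.137 | 0.056 | 0.280 | 0.620 |
| 2 | 0.125 | 0.036 | 0.261 | 0.533 |
| 3 | 0.113 | 0.022 | 0.242 | 0.442 |

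**Clock.** The time from enrolment to first dose is not given, so the effect of the enrolment clock is not sized. For resected patients, at most 6, Day -3 precedes cycle 1 Day 1 by 3 + 14 = 17 to 3 + 21 = 24 days. Sections 4.6.4 and 5 point to the later date as the start of treatment.

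**The case against.** The best defence is that the two sections can be read together. Section 4.6.4 counts disease progression as an event, and 10.4.1 gives the full definition of progression, including item (e). A death of any cause that prevents evaluation would then already be an event. This is a fair reading, but it makes the disease-death clause in 4.6.4 redundant and leaves the two time origins in conflict.

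A second defence is that Section 4.6.4 decides by counts. A count has no censoring, so with deaths scored as failures the false-go probability stays at 0.083. This also stands. The censored figures require a Kaplan-Meier cut-off that the protocol does not state, and the deaths behind them are assumed. Even on those terms, one expected death gives 0.098, inside the stated 10%.

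A reader might also take Section 11.10, which allows death as an adverse event outcome, as proof that non-disease deaths are foreseen. It is not. It is generic outcome text that sets causality to the test article aside, and a tumour death could be recorded there too.

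Nor do the documents support saying that patients enrolled but never treated are left without any provision. Sections 4.6.4 and 9.4 allow several kinds of replacement, and the primary objective concerns treated patients.

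**Conclusion.** The contradiction is real, is in the current text, and concerns the primary endpoint. It should be removed before PFS6 is read. The Simon design reproduces and is not in question.

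The size is conditional on the assumed 1 to 3 deaths. In Case A, censoring instead of failing these patients moves false-go from 0.083 to about 0.10, 0.13 or 0.18–0.19, given the added Kaplan-Meier cut-off. In Case B, counting them lowers power from 0.70 to 0.62, 0.53 or 0.44. Both cases assume constant hazards.

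Two stronger conclusions are tempting and should not be drawn. The first is that the trial's false-go rate exceeds 10%. The count rule as written does not imply that, and the net direction against the 15% rate is unknown because that rate carries no definition. The second is that patients who die of other causes would be scored as progression-free, which would give 0.20, 0.37 or 0.55 (p = 0.15 + k/26). No passage calls for that scoring, and 10.4.1 requires patients to be alive, so these figures are only an upper bound.

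**What to change.** In Section 4.6.4, replace *death due to disease* with *death from any cause*, and *study enrollment* with *start of treatment*. This matches 10.4.1 and the clock in 10.4.3 and 10.4.4. Then add four statements:

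- A counted patient who dies before 6 months from any cause is not progression-free in the Simon count.
- A death on study is not a ground for replacement in that count. Section 4.6.4 now allows replacement of patients who do not complete one cycle and have no DLT.
- For resected patients, start of treatment for PFS is cycle 1 Day 1, as Sections 4.6.4 and 5 indicate.
- The clock and death definition behind the 15% historical rate.

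The cost is two phrases and a few sentences. N = 26 and the cut-offs 2/18 and 6/26 do not change. PFS6 may come out slightly lower than with censoring: at a true 15%, by about 1.3, 2.8 or 4.4 points on average for 1, 2 or 3 such deaths. If the 15% and 30% rates turn out to exclude non-disease deaths, power falls as in Case B. The definition behind the 15% rate therefore belongs in the same amendment.

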3. PROTOCOL SYNOPSIS

Title PHASE II STUDY OF COMBINED TEMOZOLOMIDE AND

TARGETED P53 GENE THERAPY (SGT-53) FOR TREATMENT

OF PATIENTS WITH RECURRENT GLIOBLASTOMA

Study Number SGT53-02-2

Clinical Study Phase II

Phase

Clinical Sites MD Anderson Cancer Center, Texas, USA

China Medical University Hospital, Taichung, Taiwan

Study Objectives Primary:

• To evaluate the 6 month PFS in patients treated with SGT-53 in combination with Temozolomide.

Secondary:

- To assess safety of the combination of SGT-53 and Temozolomide.
- To evaluate progression free survival (PFS), and overall survival (OS) in patients in patients with recurrent or progressive GBM tumors treated with SGT-53 in combination with Temozolomide.
- To determine the anti-tumor activity of the combination of SGT-53 and Temozolomide based upon the RANO criteria in patients with recurrent or progressive GBM tumors.
- To assess nanoparticle delivery to tumor site by analysis of the presence of exogenous wt p53 in the tumor (optional procedure).
- To assess induction of apoptosis by SGT-53 in the tumor by flow cytometry or histology (optional procedure).

Study Design This is a single arm study wherein SGT-53, at a dose of 3.6 mg

DNA per infusion, will be administered. SGT-53 will be administered twice weekly [every 3rd or 4th day] in a 28 day cycle (total of 6 infusions)] starting on Day 1 (cycle 1), Day 29 (cycle2) and Day 57 (cycle 3). In those patients who undergo the optional surgical resection, the 1st cycle of SGT-53 and TMZ will start 14-21 days post operatively after having recovered from the effects of

surgery. Temozolomide will be administered by mouth daily on days 9-13 of each cycle at 150mg/m2 (cycle 1), and 200mg/m2 as tolerated for cycle 2 and beyond provided the patient meets the criteria for non-hematological toxicity, ANC and platelet counts... Patients who are responding to treatment (at least stable disease by RANO) may receive three additional cycles of SGT-53/Temozolomide therapy at investigator's discretion. Alternatively, they may continue on Temozolomide alone at investigator's discretion.

Optional Surgical Resection for Tumor Analysis:

Confidential

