4.5.2. Patient Population

The target study population is subjects with confirmed glioblastoma or gliosarcoma who have proven tumor recurrence or progression.

This study will enroll males or females aged 18 years or older with recurrent GBM or GS who may benefit from receiving SGT in combination with a cyclical TMZ. Eligible patients must have histological confirmation of GBM or GS and a diagnosis of recurrent disease with an interval of at least 3 months after radiotherapy plus TMZ. For patients who have had surgery, there must be an interval of at least 14-21 days post operatively and having recovered from the effects of surgery for the recurrent disease before initiation of cyclical treatment.

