4.6 Study Design

Based on efficacy and overall safety demonstrated in preclinical studies and the first-in-man Phase Ia and Phase Ib study in combination with docetaxel, SynerGene Therapeutics, Inc. proposes to perform a Phase II clinical study of the combination SGT-53 and temozolomide in subjects with confirmed glioblastoma who have proven tumor recurrence or progression. The goals of the proposed clinical study are to determine the anti-tumor activity of the combination

of SGT-53 and temozolomide by RANO and by evaluating the 6 month PFS; PFS and, OS and by evaluating the safety of the combination of SGT-53 and temozolomide.

The goals of the optional surgical resection are to demonstrate the nanoparticle delivery of systemically administered SGT-53 to tumor in GBM patients and to assess induction of apoptosis by SGT-53 in the tumor. Participation in the optional surgical resection will be at the discretion of the subject and investigator.

Based on the pre-clinical intra-tumoral half-life, in Phase Ia SGT-53 was given as a twice-weekly intravenous infusion over 1.5-2 hours, depending on dose level. The time of infusion can be extended in the event of infusion reactions (see Section 9.3.2); however infusion of the study agent must be completed as soon as possible, but no longer than eight hours after dilution in dextrose.

Below is the schedule of treatment:

This is a single arm study wherein SGT-53, at a dose of 3.6 mg DNA per infusion, will be administered. Patients will receive SGT-53 every 3rd or 4th day in 28 day cycles (total of 6 infusions) starting on Day 1 (cycle 1), Day 29 (cycle2) and Day 57 (cycle 3). Temozolomide will be administered by mouth daily on days 9-13 of each cycle at 150mg/m2 (cycle 1), and 200mg/m2 as tolerated for cycle 2 and beyond provided the patient meets the criteria for non-hematological toxicity, ANC and platelet counts (as given in 9.7.2). In those patients who had a surgical resection, the 1st cycle of SGT-53 and TMZ will start 14-21 days post operatively and having recovered from the effects of surgery.

Patients who are responding to treatment (at least stable disease by RANO) may receive three additional cycle of SGT-53/Temozolomide therapy at investigator's discretion. Alternatively, they may continue on Temozolomide alone at investigator's discretion.

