- 1. Signed informed consent prior to any study-mandated procedure.
- 2. Histologically confirmed glioblastoma or gliosarcoma in first, second or third relapse. A pathology report constitutes adequate documentation of histology for study inclusion. Subjects with an initial diagnosis of a lower grade glioma are eligible if a subsequent biopsy is determined to be glioblastoma. The amount of prior systemic therapy for this population is, nevertheless, restricted to three regimens.
- 3. Radiographic demonstration of disease progression following prior therapy (RANO criteria)
- 4. Measurable disease on MRI performed within 14 days prior to registration. Baseline MRIs for subjects who underwent salvage surgery after first or second relapse must be obtained ≥ 4 weeks after the procedure.
- 5. Male or female patients \geq 18 years of age.
- 6. Recurrent disease with an:
 - \Box interval of ≥ 3 months following radiotherapy + temozolomide;

- interval of \geq 14 days between end of surgery and start of protocol therapy for patients who have undergone surgery for recurrent disease.
- 7. Patients who tolerated previous administration with temozolomide, i.e.,during adjuvant Temozolomide, no dose reductions below the starting dose were required due to treatment-related toxicities
- 8. Recovery from the effects of prior therapy, including the following:
 - Four weeks from cytotoxic agents (3 weeks from procarbazine, 2 weeks from vincristine)
 - 6 weeks from nitrosoureas (CCNU, BCNU)
 - Four weeks from any investigational agent
 - One week from non-cytotoxic agents
 - 12 weeks from radiotherapy to minimize the potential for MRI changes related to radiation necrosis that might be misdiagnosed as progression of disease, or 4 weeks if a new lesion, relative to the pre-radiation MRI, develops that is outside the primary radiation field
- 9. Karnofsky performance status \geq 60% (see Section 18.3. for details).
- 10. Complete blood count (CBC)/differential at screening (within 7 days of study initiation), with adequate bone marrow function as defined by: absolute neutrophil count (ANC) \geq 1,500/ μ L; platelets \geq 100,000/ μ L; hemoglobin \geq 10 g/dL.
- 11. If patient is receiving steroids, must be on stable or decreasing steroid dose within 5 days prior to treatment initiation with SGT-53.
- 12. Patients must be willing to forego other cytotoxic and non-cytotoxic drug or radiation therapy against the tumor while enrolled in the study.

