10.2. Evaluation During Study

The starting dose of SGT-53 will be 3.6 mg of DNA. If necessary, dose de-escalation for SGT-53 will proceed according to the dose de-escalation scheme in Table 9.7.3 above. Assessment of DLTs will be made based on the first cycle (4 weeks of treatment). At the end of the first cycle, if no DLT are observed, additional patients may be enrolled and treated simultaneously. If the first patient experiences a DLT in the first cycle (4 weeks), then only one additional patient will be enrolled and evaluated for DLT. If the second patient does not experience DLT in the first cycle (4 weeks), then additional patients may be enrolled simultaneously.

10.2.1. Patients with Optional Surgical Resection for Tumor Analysis:

Beginning 5 days prior to scheduled surgical resection of their recurrent glioblastoma, patients will initiate 3.6mg DNA dosing/infusion with SGT. Dosing will continue through the day before surgery.

• One portion of the surgical section will be saline rinsed and flash frozen for measurement of exogenous wt p53 in tumor tissue, one portion will be immediately formalin-fixed for evaluation of PD biomarkers of activity of SGT-53 including but not limited to Annexin V and TUNEL staining. In addition, one portion of fresh tissue will be used for flow cytometry and/or immunohistochemistry analysis to determine the level of apoptosis in Cancer Stem Cells (CSC) and bulk tumor cells. Any remaining tumor tissue from an earlier procedure will be collected and stored in a research tissue bank at Georgetown University or the clinical site.

Following surgery, an MRI scan should be done no later than 72 hours from the time of surgery.

Following recovery from surgical resection (POD ~14-21), patients will restart SGT-53 and TMZ on the morning of Cycle 1 Day 1 (C1D1). Each cycle will consist of 28 days. Patients will return to the clinic for twice weekly (every 3rd or 4th day) infusions of SGT-53 for three weeks (see treatment schedule diagram in section 9.1.1). Temozolomide will be taken daily by mouth daily on days 9-13 of each cycle. During week 4 of each cycle the patient will not receive any treatments. Patients will return to the clinic on Day 29 (C2D1) and Day 57 (C3D1) for evaluation. If the drug has been well tolerated, continued dosing will be permitted even if they appear to be progressing.

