Patients will be monitored for response and disease progression with MRI brain scans every 2 cycles (8 weeks) and/or at the end of cycle 3, or earlier if progressive disease is suspected.

All patients who participate in this study will continue treatment with SGT-53 and TMZ after surgery. The following conditions should be satisfied before initiation of treatment with SGT:

- 1) They have recovered from the effects of surgery including adequate wound healing.
- 2) A brain MRI should be done no later than 72 hours in the immediate post-operative period to best assess the extent of residual measurable disease post-operatively.
- 3) The patient has followed the study requirements for birth control and pregnancy testing since the initial pre-operative doses of SGT and TMZ.
- 4) Post-operatively, patients must have adequate bone marrow function (absolute neutrophil count > 1,500/ μ L and platelet count of >100,000/ μ L), normal coagulation profile (PT/PTT), adequate liver function (SGPT, SGOT, and alkaline phosphatase <2.5 times upper limit of normal and bilirubin < 1.5 X upper limit of normal), adequate renal function (BUN or creatinine <1.5 times upper limit of institutional normal within 7 days prior to starting therapy.
- 5) The patient continues to meet all the eligibility criteria of the study outlined above.

10.2.2. Patients Not undergoing Surgical Resection:

Patients who have had surgery for recurrent glioblastoma will follow the guidelines listed above for patients with optional surgical resection for tumor analysis.

If no surgery has been performed, patients will start SGT-53 and TMZ on the morning of Cycle 1 Day 1 (C1D1). Each cycle will consist of 28 days. Patients will return to the clinic for twice weekly (every 3rd or 4th day) infusions of SGT-53 for three weeks (see treatment schedule diagram in section 9.1.1). Temozolomide will be taken daily by mouth daily on days 9-13 of each cycle. During week 4 of each cycle the patient will not

receive any treatments. Patients will return to the clinic on Day 29 (C2D1) and Day 57 (C3D1) for evaluation. If the drug has been well tolerated continued dosing will be permitted even if they appear to be progressing.

Patients will be monitored for response and disease progression with MRI brain scans every 2 cycles (8 weeks) and/or at the end of cycle 3 or earlier if progressive disease is suspected.

10.2.3. All Patients:

Evaluations done at each clinic visit are detailed in Section 18.1.

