18.1.2. Patients Who Undergo Surgical Resection for Tumor Analysis

TYPE OF EVALUATION	Baseline Screen	Pre	e- Surg	ery												(Cycle :	1									-
		D-3	D-2	D-1	D1	D2	D3	D4	D5	D6	D7	D8	D9	D10	D11	D12	D13	D14	D15	D16	D17	D 18	D 19	D 20	D 21	D 22	D23- D28
Informed Consent	Х																										
Physical Examination ¹	Х	х			Х							Х							х							Х	
Symptom- oriented Exam ¹				Х				Х							х							х					
ECG ²	Х	Х	Х		Х							Х															
Limited ECHO	Х																										
Vital Signs	Х	Х		Х	Х			Х				Х			Х				Х			Х				Х	
Performance Status	Х	х		Х	Х			Х				Х			Х				х			Х				Х	
Medical History³	Х	Х		Х	Х			Х				Х			Х				х			х				Х	
Hematology ^{4 9}	Х	Х			Х							Х							Х							Х	
PT/PTT, D- dimer ⁵	Х		х		Х							Х							х							Х	
Chemistries ^{6, 9}	Х				Х							Х							Х							Х	
Urine Analysis	Х				Х																						
Serum Pregnancy Test	х																										
MRI Scan ⁷	Х																										
SGT-53 Administration ⁹		Х		х	Х			Х				Х			Х				х			х					
TMZ Administration													х	Х	Х	Х	Х										

¹ Physical examination will be done on 1st visit of each week. A symptom-oriented examination will be done on the intervening study visits only if necessary. .

² ECG will be performed at baseline; 2 hours and 24 hours after the 1st SGT-53 infusion; weekly (2 hours post-infusion) during the first 2 weeks of Cycle 1 and at the EOT visit when the patient goes off study. If these patients receive additional rounds of SGT-53/Temozolomide a 12-lead ECG will only be performed as necessary and the EOT visit when the patient goes off study.

Confidential

Page 103 of 108

³ Medical History includes review of concomitant medications and adverse events.

⁴ Hematology values include complete white count (CBC) with differential and platelet count.

⁵ PT/PTT, and D-dimer for the first two subjects: at baseline/screening; ~20 hours post-infusion (during the 23 hour observation period after the first SGT-53 infusion), and thereafter once a week during Cycle 1, once in two weeks during Cycles 2 and 3; and at the exit visit. When blood chemistries are not being assessed on this same day LDH will also be determined.
PT/PTT, D-dimer and LDH for subsequent subjects: at baseline/screening; at Cycle 1, ~20 hours post-infusion 1 (during the 23 observation period after the first infusion); and at the exit visit. When blood chemistries are not being assessed on this same day, LDH will also be determined.

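### For on-study resection the only scan labelled baseline is pre-operative, so surgical debulking can be scored as response; separately, the start window for patients operated on before enrolment conflicts with inclusion 4

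*Combined protocol and SAP*

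**What the plan says.** **On-study optional resection.** Sections 4.6 and 4.6.4 allow at most 6 of the 26 patients. The option closes once 3 tumors are positive (4.6), or with 3 of the first 4 positive (8.2). In the 18.1.2 schedule the pre-operative MRI is marked in the column headed "Baseline Screen". Footnote 7 lists baseline and the scan within 72 hours of surgery as two separate time points. Section 10.2.1, condition 2, gives the purpose of the 72-hour scan: "to best assess the extent of residual measurable disease post-operatively". Section 10.4.2 defines partial response as a decrease from baseline held for at least 4 weeks, and reports the response rate at 6 and 12 months after starting treatment. Section 10.4.1 judges progression against the smallest earlier measurement, which it describes as baseline or best response.

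**Surgery before enrolment.** Section 6.1, inclusion 4: "Baseline MRIs for subjects who underwent salvage surgery after first or second relapse must be obtained ≥ 4 weeks after the procedure". Section 10.2.2: "Patients who have had surgery for recurrent glioblastoma will follow the guidelines listed above for patients with optional surgical resection for tumor analysis". The guidelines it points to, in 10.2.1, say: "Following recovery from surgical resection (POD ~14-21), patients will restart SGT-53 and TMZ". Section 4.6, repeated in section 9, is equally broad: "In those patients who had a surgical resection, the 1st cycle of SGT-53 and TMZ will start 14-21 days post operatively". The synopsis is narrower: "In those patients who undergo the optional surgical resection, the 1st cycle of SGT-53 and TMZ will start 14-21 days". Inclusion 6 asks for at least 14 days between surgery and treatment, and section 4.5.2 says "there must be an interval of at least 14-21 days post operatively".

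**The concern.** The main issue is the reference scan. If the pre-operative MRI is the RANO baseline, the operation itself shrinks the measured tumor before cycle 1. A patient whose residual tumor is merely stable on treatment can then meet the size criterion for partial response. RANO anti-tumor activity is a secondary endpoint, and in a single-arm study of 26 patients a few surgical responses would visibly change the reported rate.

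The lesser issue is that sites hold two instructions for patients already operated on for recurrence. One sets a start at about 14-21 days after surgery. The other does not allow the baseline MRI until 28 days after surgery for first or second relapse.

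**Working it through.** **1. The plan's own figures.** The plan gives no expected response rate to reproduce. Its Simon design in 4.6.4 (stop at 2 or fewer of 18; fail at 6 or fewer of 26) does reproduce. The exact binomial probability of success is 0.0826 at a PFS6 of 15% (stated limit 10%) and 0.7007 at 30% (stated 70%). Nothing below changes it.

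**2. When debulking alone meets the partial-response size threshold.** Let r be the fraction of enhancing area resected (not given, so assumed). Let g be the on-treatment area divided by the 72-hour residual. By 18.2, stable against the 72-hour scan means 0.5 < g < 1.25. Partial response against the screening scan needs g(1 − r) ≤ 0.5, that is g ≤ 0.5/(1 − r).

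| r | g must be at most | Meaning |
|---|---|---|
| 0.4 | 0.5/0.6 = 0.83 | residual must shrink by 17% |
| 0.5 | 0.5/0.5 = 1.00 | unchanged or smaller residual qualifies |
| 0.6 | 0.5/0.4 = 1.25 | the whole stable range qualifies |

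Section 10.4.2 prints a strict more-than-50% decrease, while 18.2 uses at least 50%. At r = 0.5 an unchanged residual therefore qualifies only under 18.2. The r = 0.6 row is unaffected.

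**3. Can the 4-week condition be met?** MRIs are marked in days 23-28 of cycles 2 and 3, which are study days 51-56 and 79-84. They are 79 − 56 = 23 to 84 − 51 = 33 days apart, so two stable scans can satisfy it when at least 28 days apart. Items b to f of the partial-response definition must also hold.

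**4. Size.** The ceiling, with every resected patient scored a responder:
- 3/26 = 11.5%
- 4/26 = 15.4%
- 6/26 = 23.1%

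Because 10.4.2 reports response at 6 and 12 months, a more realistic 6-month figure counts only resected patients still progression-free then. Assume they follow the protocol's PFS6 values of 15-30% and that all of those are scored as partial responses through debulking:
- 6 patients: 6 × 0.15 = 0.9 to 6 × 0.30 = 1.8 patients; divided by 26, 3.5 to 6.9 points.
- 3 patients: 0.45 to 0.9 patients; divided by 26, 1.7 to 3.5 points.

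**5. Timing for surgery before enrolment.** The earliest inclusion 4 MRI is day 28 and the 10.2.1 start is about day 14-21. The scan therefore falls 28 − 21 = 7 to 28 − 14 = 14 days after that start. The number of patients affected is not given.

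**6. Age of the 72-hour scan at cycle 1 day 1.** From 14 − 3 = 11 to 21 − 0 = 21 days.

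**The case against.** **On the reference scan.** The text leans toward a post-operative reference. The 72-hour MRI exists to measure residual disease, condition 5 of 10.2.1 re-applies eligibility (including measurable disease) after surgery, and cycle 1 day 1 is the first post-surgical infusion. A careful site might well use the 72-hour scan. That stands as a reason to expect less harm than the literal reading implies. However, no sentence makes it the RANO baseline, and the schedule attaches that label to the other scan. It is also true that response carries no hypothesis or threshold: the decision rule uses the PFS6 count.

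A reader might infer that PFS6 is biased as well. The documents do not support that. Progression is measured from the smallest earlier value, and the 72-hour scan can be read as that value. Section 10.4.1 names only baseline or best response, so the point should be made explicit, but no PFS6 effect is shown. A reader might also say that no baseline is named at all. That is too strong, because the screening scan carries the label.

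**On earlier surgery.** A reader might infer that such patients cannot be enrolled within the rules. That does not hold. The inclusion 4 MRI precedes registration, inclusion 6 and 4.5.2 set minimums, the 10.2.1 window is approximate, and a start at day 28 or later satisfies eligibility. Section 10.2.1 also begins SGT-53 before the operation, which is impossible for someone already operated on, so sites must apply only the parts that fit. What remains is a literal conflict whose practical result is a wait, a query or a deviation.

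**Conclusion.** The main point holds: as written, the response rule can count surgical removal as partial response in on-study resection patients. The 11.5 to 23.1 points are ceilings, not estimates. The expected 6-month inflation is about 3.5 to 6.9 points with 6 patients, or 1.7 to 3.5 with 3. This rests on the assumed 15-30% progression-free rate in resected patients, on enough tumor being resected, and on all those progression-free being scored as partial responses. The fraction resected is unknown.

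The timing conflict for earlier surgery is real but minor. It is a contradiction in instructions of at least 7 days, limited to surgery for first or second relapse, with no quantified effect on any endpoint.

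**What to change.** 1. In 10.2.1, 10.4 and 18.1.2, state that for on-study resection patients the existing MRI within 72 hours of surgery is the RANO baseline for response and the starting reference for progression. For all other patients it is the pre-registration MRI, including after surgery for third relapse, which the 4-week rule does not mention.
2. In 4.6, section 9 and 10.2.2, limit the 14-21 day window and the 72-hour MRI to the on-study optional resection, as the synopsis does. For surgery before enrolment, require at least 14 days and a start only after the inclusion 4 MRI.
3. In 10.2.1, condition 5, state that the 4-week rule does not apply to the on-study resection.

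These are wording changes: no added scan, and no change to the sample size or Simon boundaries. The first has a consequence to accept knowingly. The 72-hour scan is 11 to 21 days old at cycle 1 day 1, so growth before treatment counts toward progression and can affect PFS6 in up to 6 patients, although the smallest-measurement rule in 10.4.1 can already be read that way. An MRI just before cycle 1, used as the reference, would avoid this at the cost of one extra scan for at most 6 patients.
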